Intervention: The intervention consists of immediate thrombectomy (FlowTriever, Inari Medical or Indigo, Penumbra Inc.) without systemic/locally administered thrombolysis. Thrombectomy is performed via jugular or femoral venous access by an interventional cardiologist, interventional radiologist or vascular surgeon according to the instructions for use (IFU) for the particular device. The catheter is advanced over a preplaced guidewire across the right heart into the pulmonary arteries to the location of proximal thrombus. Procedural therapeutic anticoagulation with heparin is administered. After removal of the dilator, the thrombus is extracted by controlled volume aspiration through an aspiration catheter using a syringe or dedicated aspiration system, with multiple aspirations performed as needed. Procedural objectives will be clearly stated prior to the intervention and patient's clinical and hemodynamic status and residual thrombus will guide the investigators to determine when to terminate the procedure. Treatment success is defined as clear evidence of right ventricular Version 2.1: 16-12-2024

recompensation. The procedure must be discontinued in case of treatment failure, i.e. lack of improvement or hemodynamic deterioration, and major CDT complications such as cardiac arrest or severe haemoptysis. Complications will be solved directly, with a procedure/treatment best suitable according to the treating physician, to minimalize the risk of damage and promote patient recovery.

Main study parameters/endpoints: The primary outcome is the 30-day composite incidence of the binary endpoints of

- 1) all-cause mortality
- 2) treatment failure
- 3) major bleeding
- 4) and all-cause stroke

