Treatment failure in the first six hours after randomization is defined as life-threatening hemodynamic or respiratory deterioration. This deterioration is the clinical scenario if, following randomisation, the patient develops overt cardiorespiratory instability over at least 15 minutes necessitating CPR, escalation of respiratory support, or ECMO. After these first six hours, treatment failure will also be defined by increasing dosages of cardiorespiratory support (e.g. oxygen, catecholamines), and lack of improvement. Lack of improvement is defined by the presence of at least one of the following criteria: i) an equal or rising SCAI SHOCK stage (**Table 1**), ii) an equal or rising Fraction of Inspired Oxygen (FiO₂) level to maintain adequate oxygen saturation (i.e. \geq 92%), or iii) an equal or decreasing P/F ratio. Treatment failure will be determined every 6 hours starting at the moment of randomisation, until the patient is considered stable and transferable to the ward.

Secondary endpoints include the individual components of the primary outcome as well as DOOR at 7 days as the first secondary outcome; this is defined as (i) survival with no new severe functional limitation, no treatment failure and no adverse event; (ii) survival with new-onset severe functional limitation, but no adverse events and no treatment failure; (iii) survival with BARC3b bleeding; (iv) survival with BARC3c bleeding or ischemic stroke; (v) survival with treatment failure; and (vi) death. Further ranking will be performed by the number of days that a patient needs organ support. Organ support is defined as respiratory organ support with high-flow nasal cannula or (non-)invasive mechanical ventilation, or cardiovascular organ support with a vasopressor or inotropic agent. Other secondary outcomes include amount and mode of O₂ delivered (to be assessed at 48 hrs), ICU and hospital LOS, QoL, symptom burden, functional recovery and 1-year cost-effectiveness.

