Despite the accumulation of data from 3 studies, significant shortcomings in our understanding of mechanical thrombectomy remain, particularly in the measurement of outcomes with validated clinical impact and the likelihood for significant variability in the performance of thrombectomy procedures. Applicable guidelines do not make a difference between different thrombectomy devices and the CE approval for both devices is comparable.¹⁴ In the multicentre prospective FLASH registry of 800 American patients with intermediate-high or high risk PE treated with FlowTriever, 63% of the patients did not need an overnight stay in the ICU post-procedure, and a reduction in RV/LV ratio and in the number of patients with severe dyspnea were observed.¹⁵ Major adverse events, including major bleeding, and death occurred in 1.8% and 0.8%, respectively.

These studies highlight that the potential health benefit for patients may well outweigh the burden of a catheterization procedure including radiation exposure and contrast fluid load. Importantly, such a procedure may further include some delay in treatment time as compared to systemic thrombolysis, since thrombectomy requires the (fast) deployment of a (24/7 available) catheterization team. Other important clinical endpoints that were insufficiently explored and reported in the abovementioned studies are 'treatment failure' (a lack of improvement or deterioration¹⁶) and 'ischemic stroke', mostly from migrating emboli from the venous circulation to the arterial system through a patent foramen ovale or atrial septal defect.

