8. METHODS

8.1 Study parameters/endpoints

8.1.1 Main study endpoint

The primary outcome is the composite incidence of the binary endpoints of all-cause mortality, treatment failure, major bleeding and all-cause stroke at day 30.

Treatment failure in the first six hours after randomization is defined as life-threatening hemodynamic or respiratory deterioration. This deterioration is the clinical scenario if, following randomisation, the patient develops overt cardiorespiratory instability over at least 15 minutes necessitating CPR, escalation of respiratory support, or ECMO. After these first six hours, treatment failure will also be defined by increasing dosages of cardiorespiratory support (e.g. oxygen, catecholamines), and lack of improvement. Lack of improvement is defined by the presence of at least one of the following criteria: i) an equal or rising SCAI SHOCK stage (**Table 1**), ii) an equal or rising Fraction of Inspired Oxygen (FiO₂) level to maintain adequate oxygen saturation (i.e. \geq 92%), or iii) an equal or decreasing P/F ratio. Treatment failure will be determined every 6 hours starting at the moment of randomisation, until the patient is considered stable and transferable to the ward.

Upon establishing the outcome 'treatment failure' physicians are allowed to escalate therapy in whatever way they consider appropriate. Therapy crossover without meeting the primary outcome is not allowed. Major bleeding is defined as Bleeding Academic Research Consortium (BARC)3b and BARC3c bleeding (=intracranial haemorrhage).²¹ Ischemic stroke is defined as any stroke (National Institutes of Health Stroke Scale \geq 1).

All primary study outcomes will be adjudicated by an independent critical events committee. This committee will consist of an independent group of three individuals with pertinent expertise that reviews and adjudicates important endpoints and relevant AEs reported by study investigators. The committee will be blinded to treatment assignment and review safety event dossiers, which may include copies of subject source documents provided by study sites, for all reported cases where the primary outcome was met. Committee members may include (interventional) cardiologists, intensivists, pulmonologists, vascular medicine specialists, and (interventional) radiologists, as well as other experts with the necessary therapeutic and subject matter expertise to adjudicate the event categories outlined above.

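### After six hours, the treatment-failure rule leaves its *and* unresolved and names no reference value for an unchanged or worsening marker, so the same patient can be an event or not

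*Protocol*

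**What the plan says.** Protocol 8.1.1 defines the primary outcome as a 30-day binary composite of death, treatment failure, major bleeding and stroke. In the first six hours, failure is life-threatening deterioration. After that, "treatment failure will also be defined by increasing dosages of cardiorespiratory support (e.g. oxygen, catecholamines), and lack of improvement". The second element is spelled out: "Lack of improvement is defined by the presence of at least one of the following criteria: i) an equal or rising SCAI SHOCK stage", or FiO2 equal or rising, or P/F equal or falling. The Summary repeats this wording.

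On timing: "Treatment failure will be determined every 6 hours starting at the moment of randomisation", continuing "until the patient is considered stable and transferable to the ward". Section 8.3 schedules the SCAI stage at baseline and every six hours. It has no corresponding line for FiO2 or P/F.

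Two other places describe failure with *or*. The intervention paragraph of the Summary has "treatment failure, i.e. lack of improvement or hemodynamic deterioration" as a reason to stop the procedure, and the Introduction has "a lack of improvement or deterioration".

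The rule also steers treatment: "Therapy crossover without meeting the primary outcome is not allowed". Once the outcome is met, sections 5.3 and 8.1.1 leave further management to the physician. A blinded committee adjudicates, working from dossiers "for all reported cases where the primary outcome was met".

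**The concern.** The *and* in the post-six-hour sentence can join two requirements or list two separate ways to fail. *Equal or rising* is a comparison, but the text does not say whether the other side is the value at randomisation or the previous six-hourly check. Nor is there an exception for a marker that cannot improve further.

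This is more than derivation detail that an analysis plan can supply later. Treating teams apply the rule every six hours in an open-label trial, and a positive call opens the way to crossover. An analysis plan can re-derive a flag afterwards, but it cannot undo a crossover made under one reading. If sites read the sentence differently, the same clinical course becomes an event at one site and not at another.

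**Working it through.** **1. Does the reference value matter?** Take a patient at SCAI D at randomisation (two drugs), C at 6 h (one drug, no hypotension or hypoperfusion) and still C at 12 h. FiO2 is lower and P/F higher than at randomisation. Table 1 in 8.3 allows this course. Patient 1a has had the dose of the one drug raised since 6 h; in patient 1b it is unchanged.

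**2. Does *equal* catch a patient who is improving?** Inclusion criterion 2d requires respiratory failure but no hypotension or shock. Such a patient can be at SCAI A (SBP above 90, lactate below 2, ALAT below 200, pH at least 7.2, no vasoactive drug or device), the lowest stage. Patient 2 stays at A, is weaned from 100% to 60% FiO2 with rising P/F, and is not yet ready for the ward.

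| Patient | Reference | Lack of improvement? | Both required | Either suffices |
|---|---|---|---|---|
| 1a, dose raised since 6 h | previous check | yes, stage equal | event | event |
| 1a | randomisation | no | no event | event only if the dose rise is itself judged against the previous check |
| 1b, dose unchanged | previous check | yes, stage equal | no event | event |
| 1b | randomisation | no | no event | no event |
| 2, SCAI A throughout | either | yes, stage equal | no event | event |

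If both elements are required, the reference decides patient 1a. If either suffices, it decides patient 1b. Settling the *and* alone therefore does not settle the rule. Patient 2 is a problem only if either element suffices.

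**3. The plan's sample size.** Section 4.4 gives 0.19 and 0.46, a difference of 27.5% and an OR of 3.71. The difference implies 0.19 + 0.275 = 0.465, and (0.465/0.535)/(0.19/0.81) = 3.71, so 0.465 is used here. The normal approximation with 2:1 allocation, two-sided 5% and 80% power gives 33 + 66 (34 + 68 with 0.46). Fisher's exact test at 35/70 has power 0.805 (0.791 with 0.46), so the stated 35 + 70 reproduces. Dropout: 35/0.95 = 36.8, rounded up to 37; 70/0.95 = 73.7, rounded up to 74; total 111.

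**4. Illustration of dilution.** Let f be the share of otherwise event-free patients flagged, equal in both arms. f is assumed; the protocol gives no value. Then p = f + (1 − f) × p_true. For example, at f = 0.10: 0.10 + 0.90 × 0.19 = 0.271 and 0.10 + 0.90 × 0.465 = 0.5185. Power is by exact enumeration of a two-sided 5% Wald test on the log OR, n = 70/35.

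| f | CDT | Lysis | Power | Smallest 2:1 total for 80% |
|---|---|---|---|---|
| 0 | 0.190 | 0.465 | 0.831 | 96 |
| 0.10 | 0.271 | 0.519 | 0.705 | 135 |
| 0.20 | 0.352 | 0.572 | 0.568 | 180 |
| 0.30 | 0.433 | 0.626 | 0.447 | 240 |

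With 0.46 in place of 0.465, power is 0.818, 0.690, 0.553 and 0.433. If the planning rates already contain such flags, no power is lost.

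**5. Type I error.** The pooled planning rate is (70 × 0.19 + 35 × 0.465)/105 = 0.28. With 28% in both arms and the same four values of f, rejection is 0.047, 0.048, 0.046 and 0.045. Equal flagging does not inflate it.

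**The case against.** The strongest reply is that *and* means both. The same paragraph marks alternatives plainly elsewhere, with *or* and with *at least one*. The two places that use *or* are a rule for stopping the procedure and a background sentence, not the endpoint definition. On that reading patient 2 is no event. This stands as an argument for the likelier reading, but it does not make the sentence unambiguous, and patient 1a shows that the missing reference still matters.

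Patient 2 is also a narrow case: a 2d entrant at stage A, not yet ward-ready, with either element sufficing. That stands too. The protocol gives no share of such patients.

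On the reference, checks start at randomisation and SCAI has a baseline, so a time-zero value exists, and FiO2 is largely known at entry for 2d patients. But having a value does not make it the comparator, since the previous check is equally available. The statement in 8.3 that no biomarkers are required says nothing about FiO2, and the eCRF is not shown. A reader might infer that baseline FiO2 and P/F will not be recorded; the protocol does not establish that.

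Finally, the checks end at ward readiness, which shortens exposure, and the blinded committee can reject a wrong flag. However, it works under the same wording and on reported cases, so its described remit does not reach a case that a site never reported.

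**Conclusion.** The concern holds as a defect of definition that should be fixed; confidence is moderate. The wording supports two readings, the reference value is missing, and the reference changes classification under both. Counting a patient at SCAI A as a failure during oxygen weaning holds only if either element suffices.

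The size cannot be derived from the protocol. The power figures rest on an assumed f, equal in both arms, and on planning rates that exclude such flags. The loss may be zero.

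Three stronger conclusions may tempt a reader and are not supported:

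- **That the trial is underpowered, or needs 135 to 240 patients.** Nothing in the protocol fixes f.
- **That 21.5 of the 27.5 planned points hang on this rule.** Section 4.4 pools treatment failure with major bleeding in that figure. It does not separate out failure, still less failure after six hours.
- **That the false-positive rate is inflated.** Equal flagging leaves it at 4.5% to 4.8%. Flagging that differed by arm would bias the comparison, but the protocol gives no evidence that it will.

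**What to change.** Amend 8.1.1 and the matching Summary text:

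- **Reference.** Judge SCAI stage, FiO2 and P/F against the value at randomisation. Record FiO2 and P/F at that time if the eCRF does not already do so.
- **Best level.** Let *equal* count only for a marker that was abnormal at randomisation and is not at its best level (not SCAI A, not room air). Worsening always counts.
- **The *and*.** Replace it with explicit wording, both required or either sufficient, matching the reading that the 19% and 46% planning rates assumed. Section 4.4 does not say which that was, so the sponsor has to state it. The same sentence should say against what a support dose is increasing.

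The best-level item matters mainly if either element suffices. With randomisation as the reference, a patient who improves and then gives back part of the gain no longer counts as lacking improvement. Life-threatening deterioration still counts, because the later rule is added to the first-six-hour definition.

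The cost is a short amendment notified to the ethics committee under 12.3, possibly two eCRF fields, and re-derivation for patients already classified. No patients are added.

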5. TREATMENT OF SUBJECTS

5.1 Investigational product/treatment

The standard of care for the patients eligible for the TORPEDO-NL trial is parenteral anticoagulation and systemic thrombolysis (Actilyse® [manufactured by Boehringer Ingelheim Pharmaceuticals, Inc., Ingelheim am Rhein, Germany] 10mg bolus followed by 90mg in two hours). The intervention consists of parenteral anticoagulation and immediate CDT (FlowTriever or Indigo) without systemic or locally administered systemic thrombolysis. Thrombectomy is performed according to the IFU for the particular device and occurs via echoguided femoral or jugular venous access by an interventional cardiologist, interventional radiologist or vascular surgeon. The catheter is advanced over a preplaced guidewire across the right heart into the pulmonary arteries to the location of proximal thrombus. After removal

of the dilator, the thrombus is extracted by controlled volume aspiration through an aspiration catheter using either a syringe or the dedicated aspiration system depending on the device of choise, with multiple aspirations performed as needed. Investigators will determine when to terminate the procedure based on their assessment patients respiratory and hemodynamic status. Procedural objectives will be clearly stated prior to the intervention and respiratory and hemodynamic parameters, including pulmonary artery pressures, will be evaluated pre- and post-thrombectomy per protocol to inform each operator's decision to determine completion. Revaluation of the patient's condition should be carried out using blood loss as a reference, establishing 400 cc of blood loss as a cut-off value. The type and dosage of anticoagulant prescribed to each patient at discharge will be determined by local practice but administration will initially be parenteral for at least 24h after randomization. Participating centres have an institutionalized multidisciplinary Pulmonary Embolism Response Team (PERT) or EXPERT-PE team in place. The intervention team should have ample experience with endovascular interventions. At least one member of the intervention team should have sufficient experience with thrombectomy for PE and should have completed at least 3 full procedures (logged) with one of the devices. Procedures that have been carried out by two team members (for example, in a training setting) do count.

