8.2 Randomization, blinding and treatment allocation

A 2 (CDT: systemic thrombolysis) :1 (TT) randomisation will be applied. The randomization procedure will be web-based (castor), using randomly sized blocks consisting of 3,6 or 9 patients. Randomization will occur after the verification that a thrombectomy procedure can be started (randomisation-to-needle time) within 60 minutes. Randomization will be stratified by centre.

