8.6 Follow-up of subjects withdrawn from treatment

The primary outcome will be assessed following the principles of intention to treat (ITT). Hence, if the reperfusion treatment to which the patient is allocated to receive is not provided, the patient will still be followed for the occurrence of primary and secondary outcomes.

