10. STATISTICAL ANALYSIS

The data will be analyzed on an ITT basis in several steps. The ITT populations consist of all subjects who have been randomized, i.e. when the subject number and allocated regimen are recorded in the eCRF. Patients will be analyzed in accordance with the randomized treatment assignment irrespective of the factual implementation of the assigned treatment regimen. The baseline characteristics in each trial arm will be described. Continuous variables will be described as mean with standard deviation (SD) or median with interquartile range (IQR) for continuous variables depending on their normality of distribution. The Shapiro–Wilk test will be used to assess normality. Categorical variables are presented as numbers and percentages. On top of the ITT analyses a per-protocol (safety population) analysis will be performed. A detailed description of the statistical analysis will be provided in the Statistical Analysis Plan.

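### The crossover ban in section 8.1.1 makes no exception for allocated CDT that cannot be started after randomisation, leaving withdrawal from the study as the only other exit

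*Protocol*

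**What the plan says.** Section 8.1.1 lets physicians escalate as they see fit once treatment failure is established, and then adds: "Therapy crossover without meeting the primary outcome is not allowed". Section 5.3 has the same trigger: management passes to the treating physician's discretion when the primary outcome is met. Section 5.1 defines the intervention as "immediate CDT (FlowTriever or Indigo) without systemic or locally administered systemic thrombolysis".

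Section 8.1.1 also fixes when the trigger can be reached. In the first six hours, treatment failure is the situation in which "the patient develops overt cardiorespiratory instability over at least 15 minutes necessitating CPR, escalation of respiratory support, or ECMO". The wider criteria come later: "After these first six hours, treatment failure will also be defined by increasing dosages of cardiorespiratory support (e.g. oxygen, catecholamines), and lack of improvement".

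Five other provisions bear on a procedure that does not start:

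- Section 8.2: "Randomization will occur after the verification that a thrombectomy procedure can be started (randomisation-to-needle time) within 60 minutes".
- Summary, Intervention: "Complications will be solved directly, with a procedure/treatment best suitable according to the treating physician".
- Section 8.4: the investigator may take a subject out of the study for urgent medical reasons.
- Section 8.6: "if the reperfusion treatment to which the patient is allocated to receive is not provided, the patient will still be followed" for primary and secondary outcomes.
- Section 10: "Patients will be analyzed in accordance with the randomized treatment assignment irrespective of the factual implementation of the assigned treatment regimen".

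**The concern.** The protocol rests on the premise that high-risk pulmonary embolism needs reperfusion at once. Section 1 says so, and section 11.2 puts the risk of dying at up to 70% when treatment is absent or late. Section 13.2 names logistical delay of reperfusion as a main risk of the CDT arm. The obvious remedy when CDT falls through is systemic thrombolysis. It would ordinarily be available, since exclusion criterion 5 keeps out patients with an absolute contraindication to it.

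The crossover rule, taken at its word, closes that remedy until an event has happened. A team that follows the text would hold back standard care from an unstable patient. A team that gives it would commit a protocol violation or take the patient out of the study. Neither can be what the sponsor wants.

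**Working it through.** The point turns on the wording, so the provisions are set side by side. The only arithmetic is one subtraction.

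**1. Is fallback thrombolysis a crossover?** Section 5.1 excludes systemic and local thrombolysis from the CDT arm and makes thrombolysis the control treatment. Giving it to a CDT patient is therefore a switch to the other arm's therapy, which the ban covers on its face.

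**2. Does any provision exempt a procedure that never starts?**

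| Provision | What it covers | Exempts a non-start? |
|---|---|---|
| 8.2 and inclusion criterion 3 (4.2) | Feasibility before randomisation | No; it makes the case rarer |
| 13.2 | No enrolment if the team is busy, the device is unavailable or catheters are out of stock | No; also before randomisation |
| Summary, Intervention | Complications of a procedure under way | No |
| 8.6 | Allocated reperfusion not given | Follow-up only; silent on treatment |
| 8.4 | Leaving the study for urgent medical reasons | Not an exception to the ban, but an exit |

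**3. Which primary-outcome component could open the route?** Death cannot. Major bleeding and stroke meet the trigger formally, but they are largely the kind of event that exclusion criterion 5 treats as ruling thrombolysis out. In practice that leaves treatment failure.

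**4. When can treatment failure be met?**

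- From 0 to 6 hours it takes at least 15 minutes of overt instability that requires CPR, more respiratory support or ECMO. A patient who deteriorates in this way gains full discretion early.
- A patient whose shock is unchanged, or who only needs more catecholamine, does not meet that definition. Those criteria are added after six hours.
- For a patient who is merely unchanged, the failure route therefore opens at 6 hours at the earliest. The needle limit is 60 minutes, and 6 h − 1 h = 5 h. This takes lack of improvement as sufficient by itself after six hours. If rising support were required as well, the wait would be longer.

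**5. What does section 8.4 add?** It can be used at any time, and a high-risk patient left without reperfusion plausibly fits its wording. But it takes the subject out of the study, whereas 8.6 and section 10 want a patient who did not receive the allocated treatment to be followed and analysed as randomised.

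**6. Effect on the trial.** The protocol gives no expected number of non-starts and no event risk for such patients, so no power figure is derived.

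**The case against.** The strongest reply is that the ban has a narrower natural purpose. It directly follows the sentence on escalation after treatment failure, and in an open-label trial it is there to stop discretionary switching. Sections 8.6 and 10 accept that allocated treatment may not be delivered, which suggests that the authors saw non-delivery as separate from crossover. The risk is also met at its source: section 13.2 demands round-the-clock teams and a review of local protocols, and feasibility is confirmed before randomisation. A backup plan may sit in local EXPERT-PE protocols, which are not shown. Clinicians would probably treat the patient whatever the text says.

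Much of this stands, and it keeps the point small. It does not remove it. The ban has no qualifier, 5.3 repeats its trigger, and a check made before randomisation gives no rule for what fails afterwards. If clinicians treat anyway, correct emergency care becomes a violation, and centres may record it differently. Nor is this a detail to leave to a statistical analysis plan, because it is a bedside treatment rule.

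A reader might infer that a CDT patient whose procedure never starts must wait for an event and has no way to thrombolysis for six hours. The protocol does not support that. Section 8.4 offers an exit from the study at any time, and instability of 15 minutes that needs more respiratory support opens discretion earlier. The gap is the absence of a direct route within the trial for a patient who is not reperfused and does not deteriorate in the listed ways.

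**Conclusion.** The point holds as a minor safety correction. Sections 8.1.1 and 5.3 state a prohibition that, if followed, delays reperfusion in a patient who the protocol says needs it immediately. The remaining exit, 8.4, works against the intention to retain such patients.

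The five-hour figure depends on three conditions: CDT never starts, the patient neither improves nor deteriorates in the listed ways, and 8.4 is not used. The case should be rare given the 60-minute verification, but the protocol gives no rate.

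A reader might also infer a threat to power or to the trial's conclusion. The documents do not support that either. The patient is analysed as randomised, and thrombolysis given as a fallback is not itself a primary event. Events added by late reperfusion would fall in the CDT arm and so count against CDT. Any power figure would rest on assumed non-start counts and risks.

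**What to change.** Add to 8.1.1, directly after the crossover sentence, with cross-references in 5.3 and 8.6:

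> Exception: if allocated CDT has not been started and cannot be started within the 60-minute randomisation-to-needle limit or without unacceptable delay, systemic thrombolysis may be given at once. The reason and time are documented; this is recorded as non-delivery of the allocated treatment, is not in itself treatment failure, and the patient stays in follow-up and in the ITT analysis.

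The cost is a protocol amendment with one added rule and two cross-references. It needs no extra patients, procedures or analyses. The downside is a small discretionary route to switching in an open-label trial. It is contained by limiting the exception to procedures not yet started and by requiring the reason and time to be documented.
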